6.2.15 Descriptive statistics

The following statistics will be provided for continuous variables: number of observations, mean, standard deviation (SD), minimum, median and maximum. For categorical variables, frequency counts and percentages will be presented.

Mean, median and SD values will be presented to one more decimal place than the raw values. Minima and maxima will be presented as they appear. Percentages will be rounded to the nearest single decimal place, with the exception of 0 and 100, which will be presented as integers.

When descriptive statistics are reported by treatment group, data for a pooled total arm will also be reported, unless otherwise specified.

7. STATISTICAL ANALYSES

7.1 Disposition of subjects

The number of subjects will be tabulated by treatment group for the following populations:

- Screened population
- Intention-to-treat (ITT)
- Full analysis set (FAS)
- Per-protocol up to week 12 (PP1)
- Per-protocol up to week 48 (PP2)
- Safety population
- Discontinued study treatment
- Discontinued study
- Completed study

Separate tables by treatment group will also be provided for each country, and each study centre.

The disposition and number of subjects, along with reasons for screening failure, study treatment withdrawal and study discontinuations, will be listed and tabulated by treatment group. Reasons for excluding subjects from the FAS and PP populations will be listed. Data from subjects who failed at screening will be included only in the disposition tabulations and data listings.

Time to study and study treatment discontinuation will be summarised with descriptive statistics by treatment group. They will be further broken down by discontinuation reason, and when reason for discontinuation is adverse event, the preferred term.

7.2 Demographic and other baseline characteristics

Descriptive statistics (see 6.2.15) of demographic and other baseline characteristics will be tabulated in the ITT, FAS, and Safety populations, stratified by treatment group. An authorised person will code medical history and concomitant diseases using standard coding dictionaries (see 7.10.1).

The following variables will be summarized:

1. Age
2. Age (< 65, 65–74, ≥ 75)
3. Sex
4. Race
5. Ethnicity
6. Height
7. Weight
8. BMI
9. BMI (< 18.5, 18.5–24.9, 25.0–29.9, ≥ 30.0)
10. Country
11. Region (North America, rest of the world)
12. Site of onset (bulbar, spinal)
13. Edaravone use

14. Riluzole use
15. Combination of edaravone and riluzole use
16. Combination of edaravone and riluzole use by region
17. Disease duration (time from symptom onset to randomization)
18. Below median disease duration (time from symptom onset to randomization)
19. Time from symptom onset to diagnosis
20. Above median time from symptom onset to diagnosis
21. El Escorial criteria for ALS diagnosis
22. Acetylation status (slow, fast; see 7.7)
23. Acetylation status (4 groups; see 7.7)
24. Medications associated with hypotension / decrease in BP (see 7.10.1)
25. Medications associated with hypertension / increase in BP (see 7.10.1)
26. Medications associated with tachycardia / increased pulse rate (see 7.10.1)
27. Medications associated with bradycardia / decreased pulse rate (see 7.10.1)
28. Medications known to affect QT interval (see 7.10.1)
29. Cardiac or vascular abnormality (see 7.3)
30. Ischaemic heart disease (see 7.3)
31. Cardiac arrhythmias (see 7.3)
32. Cardiac failure (see 7.3)
33. Renal impairment (see 7.9.3)
34. Hepatic impairment (see 7.9.3)
35. SVC (sitting) at screening
36. Below median SVC (sitting) at screening
37. SVC (supine) at screening
38. Below median SVC (supine) at screening
39. SVC (supine) at baseline
40. Below median SVC (supine) at baseline
41. King's clinical stage at baseline (see 7.5.2.1)
42. ALSFRS-R at baseline
43. Below median ALSFRS-R at baseline
44. ALSFRS-R bulbar subdomain at baseline
45. ALSFRS-R fine motor subdomain at baseline
46. ALSFRS-R gross motor subdomain at baseline
47. ALSFRS-R respiratory subdomain at baseline
48. ALS progression rate at baseline
49. ALS progression rate at baseline (< 1 point/month, ≥ 1 point/month)
50. ALS progression rate at baseline (observed tertiles)

7.3 Medical history

Medical history will be coded with the Medical Dictionary for Regulatory Activities (MedDRA) version 23.0. Descriptive statistics will be provided by body system organ class (SOC), and preferred term (PT) for the ITT population, by treatment group.

Past findings, where the subject reports the condition has ended prior to their start of the study, and present findings, those ongoing at the start of the study, will be reported separately.

The following categories define groups of interest used in safety subgroup analyses:

1. Cardiac or vascular abnormality
2. Ischaemic heart disease (SMQ)
3. Cardiac arrhythmias (SMQ)
4. Cardiac failure (SMQ)

Both past and present findings the start of the study are included in forming these groups. See Appendix 10.1 for definitions of the search categories. If an SMQ has both a broad and a narrow definition, the narrow search will be used.

7.4 Extent of exposure and treatment compliance

The total number of exposed subjects, the total duration of study treatment exposure (continuous, and categorized both separately and cumulatively at the thresholds of ≤ 4 , ≤ 8 , ≤ 12 , ≤ 24 , and ≤ 48 weeks), and dose levels (in milligrams), averaged over the course of the study as well as at each study visit, will be reported as measures of extent of exposure.

Dose changes will be described by reporting the subject counts in the following categories:

- 1) remained at 1 mg for the entire study (“never increased”)
- 2) uptitrated to 2 mg and remained for the rest of the study (“increased and remained”)
- 3) uptitrated to 2 mg and later downtitrated to 1 mg (“increased, then decreased”).

Dose changes will also be reported by acetylation status.

Treatment compliance will be described by reporting the number of dispensed and returned study treatment capsules at each study visit. The number of subjects with treatment interruptions longer than 7 days will be reported with descriptive statistics.

Both extent of exposure and treatment compliance will be tabulated with descriptive statistics.

7.5 Efficacy

All efficacy data will be listed and tabulated by treatment group for each visit.

7.5.1 Primary efficacy variable(s)

7.5.1.1 Slow Vital Capacity

The primary efficacy variable will be change from baseline SVC, measured in the supine position (SVC [supine]), through the Week 12 visit (Visit 5). SVC is defined as the maximum volume of air that the subject can exhale slowly after slow maximum inhalation. The raw SVC volume is measured in litres. The SVC variable used in the analyses is derived from the raw SVC volume, and measured as a percentage of the predicted (normal) volume for age, height and sex. Predicted values used for the calculation are derived based on the global lung function 2012 equations (Quanjer PH et al., 2012).

SVC will be assessed in both the sitting and supine position at the screening visit. Sitting SVC is used for an inclusion criterion (sitting SVC between 60–90% of the predicted value), and supine SVC is assessed to ensure that the subject is able to perform it successfully when entering

the study. At further study visits, SVC (supine) will be assessed in the morning, before administration of the study treatment. The analysis will use the best read from up to 8 attempts, as determined by the central analysts' assessment. Only the value from the best read will be included in the study's database. If even the best read is determined to be of unacceptable quality (BTRGRCD = "U"), it will be treated as missing data in the statistical analysis.

A mixed model for repeated measures (MMRM) will be used to evaluate the change from baseline SVC (supine) in the primary efficacy analysis. The model will include: fixed effects for planned treatment, randomization stratum, study visit and a visit by treatment interaction; random effects for subject and centre; and the baseline SVC (supine) value as a covariate.

Should the model estimation fail to converge, the following steps will be taken sequentially to simplify the model structure until convergence is achieved:

1. The random effect for centre will be dropped.
2. The structure of the covariance matrix for the subject effect will be changed from unstructured to: 1) Toeplitz (TOEP); 2) first-order autoregressive (AR(1)); 3) compound symmetry (CS).

Primary efficacy will be evaluated based on the fitted model, using contrasts to obtain an estimate of the difference between the treatment and placebo at the Week 12 visit (Visit 5). Statistical significance of the Week 12 treatment difference will be tested. All SVC measurements from planned study visits prior to the Week 12 visit will be included in the estimation of the model.

SAS code in the following fashion will be used to perform the computations:

```
proc mixed data = ADEFF order = data alpha = 0.05 covtest;
  where ITTFL = "Y" and PARAMCD = "SVCPPSUP" and
    AVISIT in ("Week 2", "Week 4", "Week 8", "Week 12");
  class TRTP(ref = "PLACEBO") AVISIT STRATAR USUBJID SITEID;

  model CHG = BASE STRATAR TRTP AVISIT TRTP * AVISIT / ddfm = KR;
  repeated AVISIT / subject = USUBJID type = UN R;
  random SITEID / type = VC;

  estimate "Treatment Difference at Week 12"
    TRTP 1 -1 TRTP * AVISIT 0 0 0 1 0 0 0 -1 / cl;
run;
```

In the primary analysis, missing data are imputed using multiple imputation. As a result, the analysis above is repeated for each of the imputed data sets with the use of a by-statement. The analysis results are then pooled for inference according to the methods described in 6.2.5.

In additional analyses, data from all planned visits through 48 weeks will be included in the MMRM, and the treatment effect will be estimated with contrasts at each study visit. Further, a random slope model will be fitted, with visits' actual study days replacing the visit factor.

Changes in SVC (supine) between the last measurement while on treatment and the post-treatment measurement from their End of Study visit will be described.

Subgroup analyses will be conducted by removing the randomization stratum effect from the primary analysis model, and including the subgroup term and its interaction with treatment.

Descriptive statistics of SVC (supine) will also be presented by visit, treatment group, and angle of measurement position. The angle is categorised into three groups: 1) completely flat (0 degrees); 2) slightly elevated (up to 15 degrees); 3) unable to perform supine (> 15 degrees). The effect of angle of measurement will also be explored in an additional analysis, where the angle will be included as a factor in the primary analysis MMRM.

Time to decline from baseline SVC (supine) by $\geq 20\%$ and time to SVC (supine) $\leq 50\%$ of predicted will be assessed as secondary endpoints. Their method of analysis is described among other time-to-event endpoints in section 7.5.2.3.

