5. DETERMINATION OF SAMPLE SIZE

Sample size estimation is based primarily on supine SVC results from the study 3119001 LEVALS (Table 1). LEVALS had placebo-controlled data only up to 2 weeks, and therefore extrapolation of the results was needed. The placebo effect from phase II tirasemtiv trial BENEFIT-ALS (Shefner JM et al., 2016) was also evaluated.

Assuming a difference of at least 3.6% in change from baseline supine SVC between treatment groups and a common standard deviation of 10%, 164 evaluable subjects per group in a 1:1 allocation ratio have 90% power to detect a statistically significant difference in a two-sided, 5% α -level, two group T-test. Using a 2:1 allocation ratio, randomisation of 450 subjects to the study (approximately 300 levosimendan and 150 placebo treated subjects) allows for a total dropout rate of approximately 20%.

Table 1. Mean (SD) change from baseline SVC (supine) %-predicted in LEVALS

Treatment	2 weeks	12 weeks
Levosimendan 1 mg x 2	+2.4 (8.3)	-4.9
Levosimendan 1 mg x 1	+0.8 (8.6)	
Placebo	-3.6 (9.4)	-17.7 ¹
Placebo (BENEFIT-ALS)	-1.4	-8.5

¹ Extrapolated from the data

SD = standard deviation

Based on the dexpramipexole phase III study EMPOWER (Cudkowicz ME et al., 2013), a 12 point reduction in total ALSFRS-R score and a 15% mortality rate at 12 months can be assumed

in placebo treated patients. Assuming a 10 point decline in ALSFRS-R, with a standard deviation of 8 points, and a 20% relative improvement in survival, 450 patients provide approximately 80% simulated power to detect a statistically significant difference using a joint rank test. With 450 subjects and assuming a 48-week levosimendan event rate of 73% and hazard ratio of 0.70, time to respiratory event has approximately 70% power to detect a statistically significant difference using a log-rank test.

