6.2.2 Significance level and confidence intervals

Two-sided tests with a significance level of 5% will be used throughout the analyses. Corresponding 95% confidence intervals will be calculated for model-based contrasts, comparing the active treatment to placebo, using model-based standard error estimates.

The study has interim analyses that allow early stopping for futility, but not for efficacy. Therefore, we do not make adjustments to the significance levels in the final analyses.

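### If the primary MMRM reaches its second convergence fallback, every structure listed assumes equal variance at all visits, so the Week 12 test can exceed 5% if variance grows over time

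*SAP*

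**What the plan says.** SAP section 7.5.1.1 fits the change in supine SVC at Weeks 2, 4, 8 and 12. The sample code has the lines "proc mixed data = ADEFF order = data alpha = 0.05 covtest", "model CHG = BASE STRATAR TRTP AVISIT TRTP * AVISIT / ddfm = KR" and "repeated AVISIT / subject = USUBJID type = UN R". The planned model therefore has a separate variance for each visit, Kenward-Roger degrees of freedom and no EMPIRICAL option.

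If the model does not converge, two steps follow in sequence. Step 1: "The random effect for centre will be dropped". Step 2: "The structure of the covariance matrix for the subject effect will be changed from unstructured to" Toeplitz, then AR(1), then compound symmetry.

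Section 6.2.2 sets the error rate, "Two-sided tests with a significance level of 5% will be used throughout the analyses", and says that intervals are calculated "using model-based standard error estimates". Section 6.2.9 says that the covariance is estimated with no structure imposed beforehand. Section 6.2.10 offers a visual check of residuals as the only model check. Section 5 assumes "a common standard deviation of 10" percent for the Week 12 comparison. Its Table 1 gives phase IIa SDs at 2 weeks of 8.3, 8.6 and 9.4, and no SD at 12 weeks.

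**The concern.** Toeplitz, AR(1) and compound symmetry differ in their correlations, but each estimates a single variance for all four visits. The primary contrast uses Week 12 alone. If Week 12 is the most variable visit, the pooled variance understates its error and the test rejects too often. Kenward-Roger does not correct this. It adjusts for small-sample uncertainty within the assumed structure, not for a wrong structure.

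In a progressive disease where patients decline at different rates, the variance of change from baseline would be expected to grow with time. The SAP itself plans a random slope model for SVC. If step 2 were used and the p-value fell near 0.05, the result would be open to dispute, and changing the rule after unblinding would not be credible.

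**Working it through.** **Inputs.** Two-sided alpha 0.05 (SAP 6.2.2). Visits at Weeks 2, 4, 8 and 12 (7.5.1.1). Difference 3.6, SD 10, 450 subjects randomised 2:1, about 20% dropout, and Week 2 SDs 8.3, 8.6 and 9.4 (section 5). Ten imputations (6.2.5). Assumptions: the Week 12 SD equals the planning value of 10; the variance rises linearly from Week 2 to Week 12; 8.8 is a mid-value for the Week 2 SD.

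**The plan's own figure.** With 164 per group, the noncentrality is 0.36 × √(164/2) = 3.26. The noncentral t gives 90.15% power at 164 per group and 89.98% at 163. The stated 164 is reproduced.

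**Formula.** With complete visits and a treatment effect at each visit, the true variance of the Week 12 contrast is proportional to the Week 12 variance. Under compound symmetry the fitted variance is the mean of the four visit variances. So

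SE ratio = √(mean visit variance / Week 12 variance), and size = 2Φ(−1.96 × SE ratio).

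**Numbers in, for Week 2 SD 8.8.** The visit variances are 77.44, 81.95, 90.98 and 100, with mean 87.59. The SE ratio is √0.8759 = 0.936, and the size is 2Φ(−1.834) = 6.7%. With 300 and 150 subjects and SD 10, the correct SE is 10 × √(1/300 + 1/150) = 1.00. The model would report about 0.94.

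**Other starting values.** For Toeplitz and AR(1), the fitted matrix V is the one that minimises log|V| + tr(V⁻¹S) for true covariance S. The simulations used 4,000 complete-data trials per row, with 450 subjects, 2:1 allocation, baseline, 8 strata and no centre effect. The Monte Carlo standard error near 5% is √(0.05 × 0.95/4000) = 0.34 points.

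| SD, Week 2 to Week 12 | Mean variance | Size, formula | Size, simulated | Unstructured, simulated |
|---|---|---|---|---|
| 10 to 10 | 100 | 5.0% | 4.7–4.8% | 4.6% |
| 9.4 to 10 | 93.60 | 5.8% | 5.4% | 4.7% |
| 8.8 to 10 | 87.59 | 6.6–6.7% | 6.4–6.5% | 4.7% |
| 8.3 to 10 | 82.89 | 7.3–7.4% | 7.1–7.4% | 4.6% |
| 10 to 9 | 91.45 | 3.7–3.8% | not run | not run |

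The three structures agree closely within each row.

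**With imputation.** For 8.8 to 10, with 20% random dropout and ten imputations, the equal-variance (compound symmetry) model gave 6.1% against 5.0% for unstructured. This run used normal regression imputation in place of predictive mean matching.

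**Shape of growth.** If the variance follows a random-slope pattern instead (rising with the square of time, assumed within-subject correlation 0.5), the formula gives 5.9%, 6.8–6.9% and 7.7–7.8% for starts of 9.4, 8.8 and 8.3.

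**The heterogeneous structures.** Under that random-slope pattern, TOEPH, ARH(1) and CSH give 5.0–5.2%, 5.1–5.3% and 5.1–5.5% for the same three starts. With a common correlation of 0.5 and linear variance they give 5.0%. With a correlation of 0.8 per 4 weeks, which the unequal visit spacing makes none of them fit exactly, they give about 4.1%, slightly conservative. They were checked by formula only, not by simulation.

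**The case against.** The strongest reply is that step 2 will probably never be used. The primary model is fitted to imputed data: about 450 subjects, four visits and a 4×4 matrix with 10 parameters. The likeliest source of trouble is the random effect for 104 centres. Step 1 removes that, as does section 6.2.12. This stands, and it is why severity is low.

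Four stronger readings are tempting, and the documents do not support them.

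- *Any fallback inflates the error.* Step 1 keeps the unstructured matrix and does not have this problem.
- *The test would exceed 5%.* This needs a Week 12 variance above the average over visits. The documents set arm SDs from a 2-week crossover study against a planning value of 10. They contain no measured Week 12 SD. Growth is plausible but not shown.
- *The size is 9 to 13%.* This needs steeper growth than the documents give, such as a Week 12 SD of 12, or a Week 2 SD of 6 or less, below every Week 2 value in Table 1.
- *The 48-week SVC model is worse affected.* The steps are written for the primary model, and the SAP does not say that the 48-week analysis reuses them.

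It is also fair to say that a fallback list exists to simplify the model, and heterogeneous structures simplify it less. TOEPH has 7 parameters against 4 for Toeplitz. ARH(1) and CSH have 5 each against 2.

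**Conclusion.** The point holds conditionally. If step 2 is reached and the variance of change rises towards Week 12, the Week 12 standard error is too small and no other text in the SAP protects the primary test. On the documents' Week 2 SDs with an assumed Week 12 SD of 10 and linear variance growth, the size is about 5.4 to 7.4% on complete data, and up to 7.8% if growth is convex. The one run with dropout and imputation gave about 6.1%. The inflation is modest and the trigger unlikely, so this is a low-severity refinement of a contingency rule, not a flaw in the planned primary analysis. The simulations let baseline and stratum effects vary by visit, whereas the SAP code holds them constant across visits; this should matter little for a randomised contrast.

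**What to change.** In step 2 of section 7.5.1.1, list TOEPH, then ARH(1), then CSH, with Kenward-Roger retained, before any equal-variance structure. If an equal-variance structure is kept as a last resort, use empirical (sandwich) standard errors with it and name the degrees-of-freedom method, because Kenward-Roger adjusts the model-based errors.

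The cost is a small change to the SAP text. Each heterogeneous structure has three more variance parameters than its equal-variance counterpart, so there is a slightly higher chance that a fallback step also fails to converge. Keeping an equal-variance structure with empirical errors at the end of the list covers that case.

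### The primary MMRM fixes one baseline SVC slope across Weeks 2 to 12; a prespecified baseline-by-visit term would protect the Week 12 contrast at very small cost if that slope changes with time

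*SAP*

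**What the plan says.** SAP section 7.5.1.1 describes the primary model as having fixed effects for treatment, stratum, visit and treatment by visit, with "random effects for subject and centre; and the baseline SVC (supine) value as a covariate". The code agrees: "model CHG = BASE STRATAR TRTP AVISIT TRTP * AVISIT / ddfm = KR". `BASE` appears once, and the only term crossed with visit is treatment. The covariance is left free across the four visits: "repeated AVISIT / subject = USUBJID type = UN R".

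SAP section 6.2.9 and protocol section 8.4.3 say only that the baseline value is a covariate. None of the sensitivity analyses in SAP section 7.5.4 lets the baseline effect differ by visit.

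Missing primary data are multiply imputed (SAP section 6.2.5) from a one-row-per-subject model that uses the value at every visit.

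The sizing in SAP section 5 does not rely on baseline adjustment. It uses a two-group t-test on change: "Assuming a difference of at least 3.6% in change from baseline supine SVC between treatment groups", with "a common standard deviation of 10" percentage points, so that "164 evaluable subjects per group in a 1:1 allocation ratio have 90% power".

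**The concern.** The model is flexible where the treatment effect and the covariance are concerned, but rigid for baseline, and no reason is given. With a common slope and an unstructured covariance, generalised least squares weights the visits by information. If early visits are less variable, they dominate, and Week 12 is then adjusted with a slope learned mostly from Week 2.

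If the relation of change to baseline differs between those visits, two things follow at Week 12. Some explainable variation stays in the residual, and a chance difference in mean baseline between the arms is only partly removed. At stake is a small amount of precision in the primary contrast, in a design with little power to spare. The 48-week SVC model reuses the same structure over a longer span.

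**Working it through.** **1. The plan's own figure.** With difference 3.6, SD 10 and two-sided 5%, the normal formula gives 2 x (1.960 + 1.282)^2 x 10^2 / 3.6^2 = 162.2, so 163 per group. The exact t calculation gives 90.0% power at 163 and 90.2% at 164, so the SAP figure reproduces. At 2:1 with 20% dropout, 450 x 0.8 = 360, or 240:120, and power is 89.5%.

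**2. Inputs not in the documents (assumed).** Baseline SD 10-20; residual SD 7, 8, 9 and 10 at Weeks 2, 4, 8 and 12; adjacent-visit correlation 0.5 or 0.8; baseline slope moving linearly in time between Week 2 and Week 12.

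**3. Where the common slope comes from.** Its visit weights are w = S^-1 1 / (1' S^-1 1), where S is the residual covariance. For correlation 0.5, w = (0.51, 0.16, 0.13, 0.20). For 0.8, w = (0.79, 0.03, 0.03, 0.14). Week 2 therefore carries about half to four-fifths of the weight.

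**4. Cost at Week 12.** In large samples the Week 12 variance ratio, common slope against visit-specific slopes, is

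1 + (b12 - bc)^2 x SD_base^2 / 10^2, where bc is the weighted mean slope.

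Example: slope -0.10 to -0.20, baseline SD 15, correlation 0.8. Here bc = -0.117, the gap is 0.083, and the ratio is 1 + 0.083^2 x 225 / 100 = 1.0155. The standard error falls by 1 - 1/sqrt(1.0155) = 0.77% if the slope is freed.

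The ranges below span the two correlations. Power takes the SAP's SD of 10 as the common-slope SD at 240:120 (89.46% before the change).

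| Baseline SD | Slope, Week 2 to Week 12 | Change | Variance ratio | SE reduction | Power with the term |
|---|---|---|---|---|---|
| any | -0.10 to -0.10 | 0 | 1.0000 | 0% | 89.46% |
| 10 | -0.10 to -0.15 | 0.05 | 1.0012-1.0017 | 0.06-0.09% | 89.49-89.51% |
| 10 | -0.10 to -0.20 | 0.10 | 1.0048-1.0069 | 0.24-0.34% | 89.60-89.66% |
| 15 | -0.10 to -0.20 | 0.10 | 1.0108-1.0155 | 0.53-0.77% | 89.77-89.91% |
| 15 | -0.05 to -0.20 | 0.15 | 1.0242-1.0349 | 1.19-1.70% | 90.15-90.44% |
| 20 (extreme) | -0.10 to +0.10 | 0.20 | 1.0766-1.1104 | 3.62-5.10% | 91.50-92.28% |

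**5. Chance imbalance.** The error left in a given trial is (b12 - bc) times the baseline difference between arms. With SD 15 at 240:120, the standard error of that difference is 15 x sqrt(1/240 + 1/120) = 1.68. A 1.96-SE imbalance is 3.29 points. A slope gap of 0.05-0.10 then leaves 0.16-0.33 points, against the design effect of 3.6.

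**6. Simulation.** Complete data, 240:120, correlation 0.8, 1000 runs per scenario. Strata, centre and the imputation step were left out.

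| Scenario | Mean SE, visit-specific vs common (effect 3.6) | Rejection at 3.6 | Rejection under no effect |
|---|---|---|---|
| Equal slopes -0.10, SD 15 | 1.121 vs 1.119 | 89.9% vs 89.4% | 5.0% vs 5.0% |
| -0.10 to -0.20, SD 15 | 1.118 vs 1.126 | 90.1% vs 90.8% | 4.7% vs 4.6% |
| -0.10 to +0.10, SD 20 (extreme) | 1.117 vs 1.176 | 89.4% vs 85.9% | 5.0% vs 5.0% |

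With equal slopes the extra term costs about 0.1% in standard error. In the middle scenario it saves about 0.7%, which agrees with step 4 less that cost. Both estimates were centred on the true value within simulation error.

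**The case against.** The case against is that nothing is broken. The SAP implements what the protocol prespecified, the power calculation does not draw on baseline adjustment, and the documents contain no evidence that the baseline slope changes over time. For slope changes up to 0.10 the standard-error gain is at most 1.4% (at SD 20), which is under one power point. The middle simulation scenario shows no detectable power benefit, and a clear gain appears only in an extreme one. On this view the term is a modelling preference.

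Those facts all stand. They settle how small the point is, but not whether to make the change. The cost if the slopes are equal is about 0.1% in standard error, while the possible loss otherwise is several times that and falls on the visit being tested.

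Three stronger readings are tempting and not supported:

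- A reader might infer that the primary analysis is biased or invalid. Randomisation keeps the contrast unbiased on average, and rejection under no effect was 4.6-5.0% with either model.
- A reader might infer that baseline-related dropout distorts the primary result. Each primary data set is completed by imputation, and that imputation model does not force equal baseline slopes. The mechanism could operate in the analyses of observed data (SAP section 7.5.4.4), if dropout depends on baseline and does so differently by arm. These are sensitivity analyses, and the simulation did not cover them.
- A reader might infer that the term is certain to tighten the contrast, or that the loss converts to a definite number of subjects. The gain exists only if the slopes differ, and the documents supply none of the inputs for such a conversion.

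**Conclusion.** A cheap, worthwhile refinement, not a flaw in validity. That the model imposes one baseline slope is plain from the SAP text and code. The consequence is conditional on how the slope behaves. Over the non-extreme rows tabulated, the Week 12 variance penalty runs from about 0.1% to 3.5% and the power at stake is at most about one point. It is zero if the slopes are equal, and several percent or more only with a large baseline SD combined with a large slope change. The heavy weighting toward Week 2 rests on the assumed rise in residual variance. The size of any effect in the 48-week SVC and CGI models has not been established here.

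**What to change.** Add `BASE*AVISIT` to the MODEL statement of the primary MMRM, and state in SAP section 7.5.1.1 that the baseline effect may differ by visit. The Week 12 ESTIMATE statement needs no change, because the new term does not involve treatment. Apply the same rule to the other MMRMs that adjust for baseline, including the SVC model through 48 weeks and the CGI model tested at Week 48. Record it in section 7.11 and settle it before the treatment code is opened, since a later addition would look data-driven.

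The cost is three parameters in the primary model (four visits, less one) and about 0.1% in standard error if the slopes prove equal. By the visit schedule, the 48-week SVC model has seven post-baseline visits and would gain six parameters. CGI has five and would gain four. No new data are needed.
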